adverse events, including local infusion site tolerability, vital signs, electrocardiograms, clinical laboratory variables, and physical examinations

- Pharmacokinetics (Part B only)

The following plasma parameters will be calculated, where estimable, for ceftaroline, ceftaroline fosamil, and ceftaroline M-1: maximum plasma concentration (C_{max}), time to maximum concentration (t_{max}), area under the concentration-time curve from zero to infinity (AUC), area under the plasma concentration-time curve from zero to time of the last quantifiable concentrations [$AUC_{(0-t)}$], area under the plasma concentration-time curve from zero to 12 hours after the start of the infusion [$AUC_{(0-12)}$], apparent terminal elimination rate constant (λ_z), half-life associated with the terminal slope ($t_{1/2\lambda_z}$), mean residence time (MRT), total body clearance of drug from plasma (CL, for ceftaroline fosamil and ceftaroline [apparent CL]), volume of distribution based on the terminal phase (V_z , for ceftaroline fosamil and ceftaroline [apparent V_z]), volume of distribution at steady state (V_{ss} , for ceftaroline fosamil and ceftaroline [apparent V_{ss}]), C_{max} ratios of ceftaroline/ceftaroline fosamil and ceftaroline M-1/ceftaroline ($R_{M/D,C_{max}}$), and AUC ratios of ceftaroline/ceftaroline fosamil and ceftaroline M-1/ceftaroline ($R_{M/D,AUC}$)

Statistical methods

Due to the exploratory nature of the study, the sample size is not based on formal statistical considerations. For Part A, a sample size of 24 volunteers is considered sufficient to assess if the low-volume infusion produces an increase in the incidence of infusion site reactions (incidence >40% in subjects on active treatment). Therefore, approximately 32 volunteers will be recruited for Part A for a given treatment comparison (ie, 50 versus 250 mL or 100 versus 250 mL infusion volumes) to ensure the collection of complete data. This sample size is also sufficient to provide adequate safety data in healthy volunteers of the infusion volumes and placebo.

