2.2 Secondary objectives

The secondary objective of Part A of the study is to evaluate the safety of ceftaroline in healthy volunteers when ceftaroline fosamil 600 mg is diluted in various infusion volumes and infused into the same vein over 60 minutes every 12 hours for 72 hours (6 infusions).

The secondary objectives of Part B are:

- To characterize the PK of ceftaroline fosamil (the prodrug of ceftaroline) and ceftaroline M-1 (the microbiologically inactive metabolite of ceftaroline) in healthy volunteers following a single-dose administration of ceftaroline fosamil 600 mg diluted in various infusion volumes and infused over 60 minutes
- To evaluate the safety and tolerability of ceftaroline in healthy volunteers following a single-dose administration of ceftaroline fosamil 600 mg diluted in various infusion volumes and infused over 60 minutes

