11. EVALUATION AND CALCULATION OF VARIABLES

11.1 Calculation or derivation of safety variable(s)

11.1.1 Calculation of change from baseline

Change-from-baseline values will be calculated for the variables listed below, as the posttreatment value minus the value at baseline. The baseline values for both Part A and Part B will be as follows:

- Clinical laboratory tests: Day -1

- Vital signs (supine): Day 1 predose

If a volunteer is missing the baseline collection, the previous nonmissing evaluation will become the baseline value. If no baseline or previous-to-baseline value exist, then the baseline value will be treated as missing and no changes from baseline will be calculated.

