12.2.3 Safety and tolerability

Continuous variables (clinical chemistry, hematology, and vital signs) will be summarized using descriptive statistics (n, mean, SD, minimum, median, and maximum) by scheduled time point. Categorical variables (AEs and urinalysis) will be summarized in frequency tables (frequency and proportion).

For Part A, systemic AEs will be summarized by the active treatment received in the respective treatment period (ie, ceftaroline fosamil 600 mg in either 50 or 250 mL infusion volumes). Clinical laboratory and vital sign parameters will be summarized by scheduled assessment (Day -1 to follow-up) for all Part A volunteers overall.

For Part B, AEs will be presented by treatment (ie, ceftaroline fosamil 600 mg in 50, 100, or 250 mL infusion volumes, as applicable). Clinical laboratory and vital sign parameters will be summarized by scheduled assessment (Day -1 to follow-up) for all Part B volunteers overall.

SAEs will be collected from the time when informed consent is signed until the follow-up visit. Non-serious AEs will be collected from Day -1 (first admission period) until the follow-up visit. Adverse events that occur before the first dose of IP will be listed and flagged, but will not be included in the tabular summaries of AEs.

Adverse events will be presented by preferred term and system organ class according to MedDRA classification. Listings of SAEs and AEs that led to withdrawal will be presented and the number of volunteers who had any AEs, SAEs, AEs that led to withdrawal, AEs

judged as causally related to IP by the Investigator, and AEs with severe intensity will be summarized.

Electrocardiogram and physical examination findings will be listed only.

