12.2.5 Pharmacodynamics (Not applicable)

12.2.6 Infusion Site Reactions (Part A Only)

The occurrence of ISRs will be listed with VIP score by infusion volume/treatment combination across all assessments.

ISR incidence (number and percent of subjects) will be presented by infusion volume (50, 100, or 250 mL) and treatment (ceftaroline fosamil or placebo) combination. Incidence will also be cross-tabulated as occurrence (yes/no) across for active vs. placebo by infusion volume and treatment.

Placebo 50 mL will be presented separately to placebo 250 mL to allow the active incidence to be contrasted with its corresponding placebo.

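### Part A laboratory and vital-sign tables are pooled over the active infusion volumes, so the by-volume safety picture would rest on AEs and infusion site reactions alone

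*Supplement*

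**What the plan says.** All references are to the amended protocol; no separate SAP is among the documents.

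- **Objective.** Section 2.2 sets the Part A secondary objective: to "evaluate the safety of ceftaroline in healthy volunteers when ceftaroline fosamil 600 mg is diluted in various infusion volumes".
- **Outcomes.** The synopsis lists the safety variables as "adverse events, including local infusion site tolerability, vital signs, electrocardiograms, clinical laboratory variables, and physical examinations".
- **AEs.** Section 12.2.3: "For Part A, systemic AEs will be summarized by the active treatment received in the respective treatment period".
- **Infusion site reactions (ISRs).** Section 12.2.6: "ISR incidence (number and percent of subjects) will be presented by infusion volume (50, 100, or 250 mL) and treatment (ceftaroline fosamil or placebo) combination".
- **Laboratory and vital signs.** Section 12.2.3: "Clinical laboratory and vital sign parameters will be summarized by scheduled assessment (Day -1 to follow-up) for all Part A volunteers overall".
- **Baseline.** Section 11.1.1 gives "Clinical laboratory tests: Day -1" and, for vital signs, the predose value on Day 1. It does not say of which period, and both days occur in each of the two Part A periods.
- **AE reporting rule.** Under Section 6.3.4, a worsening in a scheduled laboratory value or vital sign becomes an AE only if it meets a seriousness criterion or leads to stopping the product. If it comes with symptoms, the symptom is reported. The reason given is that these results will be summarised in the study report.

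**The concern.** The randomised factor in Part A is the volume in which the active dose is diluted. Two of the three tabulated kinds of safety data keep that factor visible. The third, laboratory and vital signs, averages over it.

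The AE reporting rule sharpens the point. Symptom-free laboratory changes are largely kept out of the AE table on the ground that they are summarised elsewhere, and that summary does not separate the volumes. A volume-specific change without symptoms would then show in no planned table.

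There is a modest reason to look. Systemic dose is constant, but infusate concentration is not: 600/50 = 12 mg/mL against 600/250 = 2.4 mg/mL. Section 3.2 puts earlier clinical concentrations at no more than 8 mg/mL and cites animal haematology data on haemolysis in its discussion of concentration. Section 1.3 names haemolytic anaemia among the important potential risks. Table 6 includes haemoglobin, reticulocytes and bilirubin. Part A is the only multiple-dose part.

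**Working it through.** **1. Are laboratory data collected in each period?** Table 7 gives 6 chemistry and 6 haematology samples per Part A volunteer. The schedule in Table 2 gives screening 1 + 2 periods × (Day -1, discharge) + follow-up 1 = 6. Volumes: 6 × 2.5 = 15 mL chemistry, 6 × 2 = 12 mL haematology, plus 2.5 mL serology = 29.5 mL. All match Table 7. There is therefore one draw before and one after treatment in each period. Vital signs are also taken on Days 1 to 3 of each period.

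**2. Can each period be tied to one active volume?** Yes. Table 4 and Section 5.5.2 give active drug in one arm and placebo in the other, so each period has exactly one active volume.

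**3. What does pooling do to a volume-specific shift?** Let *d* be a mean shift under one active volume and 0 the shift under the other, and let *w* be the share of volunteers on the first volume. The overall mean shift is *w·d* + (1 − *w*)·0. With 24 evaluable volunteers split 12 and 12, *w* = 0.5:

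| True shift under one volume | Shift in the overall table |
|---|---|
| 0.25 SD | 0.125 SD |
| 0.5 SD | 0.25 SD |
| 1.0 SD | 0.5 SD |

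For a binary abnormality, 6/24 under one volume and 0/24 under the other show as 6/48 = 12.5% when both periods are taken together.

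**4. Where does this apply?**

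| Assessment | Volume exposure | Mixing? |
|---|---|---|
| Screening; Period 1 Day -1 and Day 1 predose | none yet | no |
| Days 2 and 3, each period (vital signs) | that period's active volume | yes |
| Discharge, each period (laboratory and vital signs) | that period's active volume | yes |
| Period 2 Day -1 and Day 1 predose | Period 1 volume, then washout | baseline for Period 2 |
| Follow-up | both volumes | cannot be assigned |

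The washout is at least 108 hours. With a half-life of 2 to 3 hours that is at least 108/3 = 36 half-lives, so Period 2 has a usable baseline of its own.

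**5. What would a split give?** With 24 completers, each volume has *n* = 24 instead of a 12 + 12 mixture at each period-day. The 95% half-width for the within-volunteer difference is *t*(0.975, *n* − 1)/√*n*: 0.42 SD of the differences at *n* = 24, and 0.36 at *n* = 32. The documents give no SD, so this stays in SD units. With no abnormality seen at a volume, the one-sided 95% upper bound is 1 − 0.05^(1/*n*): 11.7% for 0/24 and 8.9% for 0/32.

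**The case against.** **Pooling is defensible because systemic exposure is the same.** Section 1.2 expects similar exposure across volumes. Both arms are infused together, so total fluid is 50 + 250 = 300 mL in every period of Sequences 1 and 2. Only the concentration and site of the active infusion differ, which is mainly a local matter and is covered by volume in the ISR table. This stands, and it is why the likely consequence is small.

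**The vital-sign readings are poorly timed to show an effect.** On Days 1 to 3 they precede the morning infusion. On Days 2 and 3 that is about 12 − 1 = 11 hours after the previous one ended. This also stands. The laboratory discharge values are the stronger reason for the split.

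**Part B is pooled too, so this looks like a consistent choice.** The comparison does not carry over for laboratory data. Table 7 gives Part B 4 samples (screening, Day -1, discharge, follow-up), none between the two doses, so a laboratory split there is impossible. In Part A it is possible.

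**Others will look at the data.** Section 11.1.2 has laboratory and vital-sign data reviewed for other significant AEs, and Section 12.2.1 refers to individual listings. These reduce the risk of missing a marked individual case, but neither is a summary by volume.

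**Stronger readings the documents do not support.** A reader might infer that the secondary objective cannot be answered. It can: AEs and ISRs are shown by volume, the period-level data exist, and listings would allow the contrast to be rebuilt. The objective promises no between-volume laboratory contrast, and Section 12.2.1 excludes formal testing. A reader might also infer that Period 2 changes will be taken from a Period 1 baseline. Section 11.1.1 is silent, but elsewhere the protocol names the first period when it means it (Table 2 footnotes; the AE window in Section 12.2.3), so a per-period baseline is a plausible reading.

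**Conclusion.** The point holds as a gap in planned presentation. As written, the by-volume safety evaluation in Part A would rest on AEs and ISRs, while laboratory and vital-sign results, which are named safety outcomes, appear only pooled. The AE rule in Section 6.3.4 means the AE table would not catch most symptom-free changes.

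A shift confined to one volume would be roughly halved at the vital-sign assessments on Days 2 and 3 and at discharge in each period. The factor of one half assumes near-equal numbers per sequence and similar completion in both. It does not apply before first dosing or at follow-up.

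Nothing is lost from the data, and with the same dose and infusion duration a large difference is not expected. Priority is low to modest; the case for acting is that the improvement is nearly free.

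**What to change.** 1. **Section 12.2.3.** Add that Part A laboratory and vital-sign values, and changes from baseline, are also summarised by the active volume received in that period (50, 250 and, if used, 100 mL), as already planned for systemic AEs.
2. **Section 11.1.1.** State that in Part A baseline is the period's own value: Day -1 for laboratory tests, Day 1 predose for vital signs.
3. **Table layout.** Keep the overall column. Show screening and the single follow-up assessment only there, since follow-up comes after both volumes.

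The cost is two sentences and extra table columns. No new samples, volunteers or tests are needed. If a separate SAP exists, the same text can go there, provided Section 12.2.3 no longer reads as an overall summary only.

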12.2.4 Pharmacokinetics

Individual blood sample collection times, derived sampling time deviations, and concentration-time data will be listed. Pharmacokinetic data will be presented by analyte and treatment (Treatment A or E and Treatment C), as appropriate. Rounding conventions will follow Standard Operating Procedures and Work Instructions.

Plasma concentrations of ceftaroline fosamil, ceftaroline, and ceftaroline M-1 will be reported to the same precision as the source data. Plasma concentrations will be summarized by nominal time point using descriptive statistics including the population size (N for sample size and n for available data), geometric mean, geometric coefficient of variation (CV%), arithmetic mean, SD, median, minimum, and maximum.

The geometric mean is calculated as the exponential of the arithmetic mean calculated from data on a log scale. The CV is calculated as $100 \cdot \sqrt{(\exp(s^2) - 1)}$ where s is the SD of the data on a log scale.

Plasma concentrations that are below the lower limit of quantification (LLOQ) will be handled as follows:

- At a time point where less than or equal to 50% of the values are below the LLOQ (BLQ), all BLQ values will be set to LLOQ, and all descriptive statistics will be calculated.
- At a time point where more than half of the values are BLQ, the mean, SD, geometric mean, and CV% will be set to Not Determined (ND). The maximum value will be reported from the individual data, and the minimum and median will be set to BLQ.
- If all values are BLQ at a time point, no descriptive statistics will be calculated for that time point. Not applicable (NA) will be reported for SD and CV% and BLQ will be reported for mean, geometric mean, minimum, median, and maximum.
- The number of BLQ values (n below LLOQ) will be reported for each time point.

Plasma PK parameters and ratios will be summarized by analyte and treatment as appropriate using descriptive statistics including: N, n, geometric mean, CV%, arithmetic mean, SD, median, minimum, and maximum.

Individual and summarized concentration-time profiles will be depicted on linear and semi-logarithmic scales by analyte and/or treatment. Plots of geometric mean and individual

values versus treatments will be presented for ceftaroline AUC, $AUC_{(0-t)}$, $AUC_{(0-12)}$, and C_{max} . Additional graphical presentations of data will be presented as deemed appropriate.

12.2.5 Pharmacodynamics (Not applicable)

12.2.6 Infusion Site Reactions (Part A Only)

The occurrence of ISRs will be listed with VIP score by infusion volume/treatment combination across all assessments.

ISR incidence (number and percent of subjects) will be presented by infusion volume (50, 100, or 250 mL) and treatment (ceftaroline fosamil or placebo) combination. Incidence will also be cross-tabulated as occurrence (yes/no) across for active vs. placebo by infusion volume and treatment.

Placebo 50 mL will be presented separately to placebo 250 mL to allow the active incidence to be contrasted with its corresponding placebo.

12.3 Determination of sample size

Due to the exploratory nature of the study, the sample size is not based on formal statistical considerations. A sample size of 24 volunteers is considered sufficient to assess if the low-volume infusion produces an increase in the incidence of ISRs (>40%). Therefore, approximately 32 volunteers will be recruited for Part A of this study to ensure the collection of complete data. This sample size is also sufficient to provide adequate safety data in healthy volunteers of the infusion volumes and placebo.

The PK profiles of ceftaroline, ceftaroline fosamil, and ceftaroline M-1 following a single-dose iv administration of 600 mg ceftaroline fosamil (diluted in 250 mL) over 60 minutes have been characterized in previous studies. In Part B of the current study, although the infusion volumes will be different, this same dose and infusion duration will be administered across treatments and no major differences in exposures are expected. Data collected from approximately 8 volunteers is deemed adequate to characterize the PK of the 3 analytes in Treatment A (or Treatment E) and Treatment C.

13.2 Overdose

No specific information is available on the treatment of overdosage with ceftaroline fosamil. There were no reports of an acute overdose of ceftaroline in clinical studies. In the event of an acute overdose, ceftaroline should be discontinued and general supportive treatment given.

13.3 Pregnancy

All pregnancies and their subsequent outcome (spontaneous miscarriage, elective termination, ectopic pregnancy, normal birth, or congenital abnormality) should be reported to AstraZeneca using the appropriate forms.

13.3.1 Maternal exposure

Women of childbearing potential are not allowed in this study. Should a pregnancy still occur, the IP should be discontinued immediately and the pregnancy reported to AstraZeneca.

13.3.2 Paternal exposure

Pregnancy of a volunteer's partner is not considered to be an AE. However, any conception occurring from the date of dosing until 3 months after dosing should be reported to AstraZeneca and followed up for its outcome.

Appendix B
Additional Safety Information

FURTHER GUIDANCE ON THE DEFINITION OF A SERIOUS ADVERSE EVENT (SAE)

Life threatening

‘Life-threatening’ means that the subject was at immediate risk of death from the AE as it occurred or it is suspected that use or continued use of the product would result in the subject’s death. ‘Life-threatening’ does not mean that had an AE occurred in a more severe form it might have caused death (eg, hepatitis that resolved without hepatic failure).

Hospitalisation

Outpatient treatment in an emergency room is not in itself a serious AE, although the reasons for it may be (eg, bronchospasm, laryngeal oedema). Hospital admissions and/or surgical operations planned before or during a study are not considered AEs if the illness or disease existed before the subject was enrolled in the study, provided that it did not deteriorate in an unexpected way during the study.

Important medical event or medical intervention

Medical and scientific judgement should be exercised in deciding whether a case is serious in situations where important medical events may not be immediately life threatening or result in death, hospitalisation, disability or incapacity but may jeopardize the subject or may require medical intervention to prevent one or more outcomes listed in the definition of serious. These should usually be considered as serious.

Simply stopping the suspect drug does not mean that it is an important medical event; medical judgement must be used.

Examples of such events are:

- Angioedema not severe enough to require intubation but requiring iv hydrocortisone treatment
- Hepatotoxicity caused by paracetamol (acetaminophen) overdose requiring treatment with N-acetylcysteine
- Intensive treatment in an emergency room or at home for allergic bronchospasm
- Blood dyscrasias (eg, neutropenia or anaemia requiring blood transfusion, etc) or convulsions that do not result in hospitalisation
- Development of drug dependency or drug abuse.

A GUIDE TO INTERPRETING THE CAUSALITY QUESTION

The following factors should be considered when deciding if there is a “reasonable possibility” that an AE may have been caused by the drug.

- Time Course. Exposure to suspect drug. Has the subject actually received the suspect drug? Did the AE occur in a reasonable temporal relationship to the administration of the suspect drug?
- Consistency with known drug profile. Was the AE consistent with the previous knowledge of the suspect drug (pharmacology and toxicology) or drugs of the same pharmacological class? OR could the AE be anticipated from its pharmacological properties?
- Dechallenge experience. Did the AE resolve or improve on stopping or reducing the dose of the suspect drug?
- No alternative cause. The AE cannot be reasonably explained by another aetiology such as the underlying disease, other drugs, other host or environmental factors.
- Rechallenge experience. Did the AE reoccur if the suspected drug was reintroduced after having been stopped? AstraZeneca would not normally recommend or support a rechallenge.
- Laboratory tests. A specific laboratory investigation (if performed) has confirmed the relationship?

A “reasonable possibility” could be considered to exist for an AE where one or more of these factors exist.

In contrast, there would not be a “reasonable possibility” of causality if none of the above criteria apply or where there is evidence of exposure and a reasonable time course but any dechallenge (if performed) is negative or ambiguous or there is another more likely cause of the AE.

In difficult cases, other factors could be considered such as:

- Is this a recognised feature of overdose of the drug?
- Is there a known mechanism?

Ambiguous cases should be considered as being a “reasonable possibility” of a causal relationship unless further evidence becomes available to refute this. Causal relationship in cases where the disease under study has deteriorated due to lack of effect should be classified as no reasonable possibility.

Clinical Study Protocol Appendix C

Drug Substance	Ceftaroline fosamil
Study Code	D3720C00015 (P903-30)
Edition Number	1
Date	

